#### Measurement of adipocyte cell size and cell density, and capillary density

Adipocyte size and number in adipose tissue biopsy samples will be quantified after staining with hematoxylin and eosin (H&E) using MetaMorph Image Analysis software (Molecular Devices) (18, 19, 24). Similarly, We will quantify the capillary:adipocyte ratio (#capillaries/cell) and capillary density (capillaries per adipocyte cell area) using Rhodamine-labeled GSL to stain for capillaries with standard immunohistochemistry techniques (14).

Angiogenic potential (ex vivo): Quantification of angiogenic potential will be examined *ex vivo* by incubating subcutaneous adipose tissue explants in extracellular matrix components in the presence of pro-angiogenic factors as described in detail by Rojas-Rodriguez et al. (20). Under these conditions, the adipose tissue explants sprout capillaries into the extracellular matrix environment (i.e., Matrigel). We will examine capillary “sprouting” over 7 days. Quantification of capillary growth (i.e., number of capillary sprouts, growth area, and percent of tissue with growth) will be performed using ImageJ software.

Extracellular matrix remodeling in adipose tissue. We will perform immunohistochemistry techniques along with qPCR analysis on adipose tissue samples (24) to quantify expression of some key factors involved in extracellular matrix remodeling in adipose tissue. Weight gain has been reported to increase expression of Collagen I, III, and VI, as well as Secreted Protein, Acidic and Rich in Cysteine (SPARC) (11), and we will compare the expression of these factors in adipose tissue samples from our insulin resistant and insulin sensitive obese subjects.

Unbiased proteomic analysis of the phosphoproteome in skeletal muscle. The untargeted phosphoproteomic

analyses will be performed in [name] laboratory at Wayne State University (~1h drive from [name] lab at the University of Michigan). [name] will be performing the proteomic analysis on skeletal muscle samples collected in this study. We will bring de-identified muscle samples to [name] laboratory at Wayne state for this analysis. [name] is an expert in proteomic analysis of skeletal muscle samples. Protein isolation, and in-solution trypsin digestion and phosphopeptide enrichment using titanium dioxide ( $\text{TiO}_2$ ) will be performed as described previously by [name] (10, 28). Mass spectrometry, data analysis and bioinformatics will all also be performed as detailed previously by [name] (10, 28). We will aliquot muscle protein lysates and use some aliquots to perform western blot analysis on the proteins with significant differences between our insulin resistant and insulin sensitive subjects. We will assess the proteomic findings in context of the subjects' muscle fiber composition, which we will assess using standard immunohistochemistry methods.

### Statistical analysis

Student's t-test will be used to assess statistical significance of our major endpoints between **NIR** and **IR**. In addition, we will perform linear regression analyses using our entire cohort of subjects (**NIR**, **MIR**, and **IR**) to assess relationships between each of our major endpoints and insulin resistance. Finally, we will also conduct multiple regression analysis using our entire cohort to assess the relative contribution of each of our major endpoints to the variance of insulin resistance. A *P* value of  $\leq 0.05$  will be considered statistically significant.

For our untargeted analyses, the false discovery rate (FDR) for both proteins and peptides will be set to 0.01. In addition, only phosphosites with a localization probability greater than 0.75 will be considered as "identified", a threshold used commonly in phosphoproteome studies. To be used in comparisons between groups, phosphorylation sites need to satisfy the following criteria: 1) identified in more than half of the samples; and 2) with a fold change (or difference) greater than 1.5 between comparisons. For comparisons between groups for both our untargeted and target endpoints, a Student's t-test will be used to assess statistical significance of our major endpoints for our primary comparison between the **NIR** and **IR** groups. In addition, we will perform simple linear regression analyses to assess relationships between each of our major endpoints and insulin resistance. Finally, we will also conduct multiple regression analysis to assess the relative contribution of each of our major endpoint measures to the variance of insulin resistance. A *P* value of  $\leq 0.05$  will be considered statistically significant.

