### **Subject stratification**

As noted above, subjects will be stratified into 3 groups based on their degree of insulin resistance, as defined by their glucose disposal rate (GDR) measured via hyperinsulinemic/euglycemic clamp during the experiment.

- 1) ***“Insulin resistant” [IR]*** (GDR  $< 28 \mu\text{mol/kg fat free mass [FFM]/min}$ ),
- 2) ***“Mildly insulin resistant” [MIR]*** (GDR  $> 28 \mu\text{mol/kg FFM/min}$  and  $< 40 \mu\text{mol/kg FFM/min}$ )
- 3) ***“Non-insulin resistant” [NIR]*** (GDR  $> 40 \mu\text{mol/kg FFM/min}$ ).

The “cutoff points” used to stratify our subjects into these 3 groups were defined by Stern et al., (25). Stern, et al., used a statistical approach using hyperinsulinemic-euglycemic clamp data from 2,138 ethnically diverse non-diabetic subjects (insulin infusion rate =  $40 \text{ mU/m}^2/\text{min}$ , which is the same as we propose here). They defined the “optimal insulin resistance cutoff” as being  $< 28 \mu\text{mol/kg FFM/min}$ . We will make every effort to closely balance subject characteristics across the three study groups (including sex).

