### Sample size calculations

**Specific Aim #1:** The number of subjects necessary to find statistical differences between our insulin resistant (**IR**) and our non-insulin resistant (**NIR**) groups in major endpoints of this study was calculated based on mean and standard deviation values derived from our preliminary studies and our previous publications (18, 24). The sample size calculations (Table 2) indicate that at least 17 subjects will be required for each group in this study. Our primary comparisons will be between the **IR** and **NIR** groups, but subjects will also be stratified into the **MIR** ("mildly insulin resistant") group. Based on previous work (27), we anticipate that our subjects will be stratified relatively evenly into our three study groups (i.e., **NIR**, **MIR**, and **IR**), but it is quite possible this may not be the case. Therefore, we plan to enroll a total of 60 subjects into this study in order to end with at least 17 subjects in both the **IR** and **NIR** groups.

Table 2. Sample size calculations for Specific Aim #1

	Power	$\alpha$	Expected $\Delta$ (%)	Estimated SD (%)	# of subjects
Fatty acid Ra	0.8	0.05	35%	30%	13
Adipogenic capacity assays	0.8	0.05	20%	20%	17
Adipocyte cell size	0.8	0.05	25%	25%	17

**Specific Aim #2:** The number of subjects necessary to find statistical differences between **IR** and **NIR** groups in key endpoints of the studies designed to address Specific Aim #2 was calculated based on mean and standard deviation values derived from our preliminary studies, work published in our previous publications (15, 16) and from previous work (14). For Specific Aim #2, we will only perform the analyses on samples from subjects in the **IR** and **NIR** groups. The sample size calculations (Table 3) indicate that we will need at least 17 subjects in both groups. For our proteomic analyses, we will use the samples collected from the number of subjects required for our targeted analyses to be statistically significant.

Table 3. Sample size calculations for Specific Aim #2

	Power	$\alpha$	Expected $\Delta$ (%)	Estimated SD (%)	# of subjects
Macrophage infiltration	0.8	0.05	20%	20%	17
Cytokine abundance	0.8	0.05	50%	40%	12
Muscle ceramide concentration	0.8	0.05	20%	20%	17

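### The planned Student's t-test can miss its nominal 5% level if the IR and NIR groups end up unequal in both size and spread; naming Welch's test in advance removes the risk at little cost

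*Combined protocol and SAP*

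**What the plan says.** The first paragraph of the Statistical analysis section says "Student's t-test will be used to assess statistical significance of our major endpoints between" NIR and IR. The second paragraph repeats the choice: "For comparisons between groups for both our untargeted and target endpoints, a Student's t-test will be used to assess statistical significance". Significance is set at P ≤ 0.05. Neither paragraph mentions an unequal-variance version, a variance check, a transformation or a rank-based fallback.

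Under Subject stratification, membership follows from the measured glucose disposal rate, with fixed cutoffs at 28 and 40 µmol/kg FFM/min. The balancing sentence there covers subject characteristics, sex included, but not group sizes.

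Under Sample size calculations, the authors write that "we anticipate that our subjects will be stratified relatively evenly into our three study groups" and then add "but it is quite possible this may not be the case". Their response is a larger total, aimed at the two groups to be compared: "we plan to enroll a total of 60 subjects into this study in order to end with at least 17 subjects in both the" (the sentence ends by naming those two). No quota, cap or continue-until-filled rule is given. Tables 2 and 3 list one SD per endpoint, as a percentage, and one required number per group.

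**The concern.** Student's t-test pools the two sample variances. With equal group sizes this does little harm even if the true variances differ. With unequal sizes the pooled variance is dominated by the larger group, so the standard error is too small when the smaller group is the more variable and too large when it is the less variable.

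Every primary NIR–IR comparison rests on this test, and the ratio of the group sizes will not be known until the clamps are done. If sizes and spreads both turn out to differ, P values are too small or too large by an amount and in a direction that cannot be foreseen. Changing the test at that stage would be a data-driven choice.

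**Working it through.** **1. The plan's own figures.** For a two-sided two-sample test with equal n and a common SD, the normal approximation is n = 2(1.96 + 0.8416)² ÷ (Δ/SD)². With Δ/SD = 1 this is 15.70, or 16. The t-based calculation gives 16.71, so 17, as in four rows of Tables 2 and 3. Fatty acid Ra (35/30) gives 12.57, so 13. Cytokine abundance (50/40) gives 11.09, so 12. All six stated numbers reproduce, so the tables are sound for a common SD.

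**2. How uneven the groups could be.** Suppose each of the three groups has a true share of one third, which is the plan's expectation. Then 60 subjects yield at least 17 in both IR and NIR with probability 0.67. The larger-to-smaller size ratio is at least 1.5 in about 22% of studies and at least 1.67 (25/15) in about 12%. A split as extreme as 28/12 occurs in about 1% or less. If the true shares of the two compared groups were 25% and 40% (an assumption), the chance of at least 17 in both falls to 0.30.

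**3. Why the level shifts.** For group sizes n₁, n₂ and SDs s₁, s₂, Student's test on average uses the variance [((n₁−1)s₁² + (n₂−1)s₂²)/(n₁+n₂−2)] × (1/n₁ + 1/n₂). The correct variance is s₁²/n₁ + s₂²/n₂. Let R be the ratio of the first to the second. The true two-sided level is then roughly P(|Z| > 1.96√R).

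- 17/26, SD 1.5 in the smaller group and 1 in the larger: pooled variance (16 × 2.25 + 25)/41 = 1.488; times 0.0973 = 0.1448. Correct: 2.25/17 + 1/26 = 0.1708. R = 0.847, level about 7.1%.
- 17/26, SDs reversed: pooled variance (16 + 25 × 2.25)/41 = 1.762; times 0.0973 = 0.1714. Correct: 1/17 + 2.25/26 = 0.1454. R = 1.179, level about 3.3%.
- 20/20, any SDs: R = 1, level about 5%.

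**4. Simulated level of Student's test** (normal data, equal means, nominal two-sided 5%, assumed SD ratios 1.2 to 1.5):

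| Split | Larger SD in smaller group | Larger SD in larger group |
|---|---|---|
| 20/20 | 5.0–5.2% | same by symmetry |
| 17/20 | 5.4–5.9% | about 4.4% at ratio 1.5 |
| 17/26 | 5.9–7.0% | 4.2–3.4% |
| 15/25 | 6.3–7.5% | 4.1–3.2% |
| 12/28 (extreme) | 6.8–9.4% | 3.6–2.2% |

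Welch's test stays at 4.8–5.2% throughout. With equal SDs, Student's test is at about 5% at every split. Simulation noise is a few tenths of a point: 15/25 at ratio 1.2 came out between 5.9% and 6.3%.

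**5. Effect on power if the SD is proportional to the mean** (an assumption). Take the cytokine row with means 100 and 150 and SDs of 40% of each, so 40 and 60. With 25 in the higher-mean group and 15 in the lower, the pooled variance is (14 × 1600 + 24 × 3600)/38 = 2863, and the standard error is √(2863 × 0.1067) = 17.5. The correct value is √(1600/15 + 3600/25) = 15.8. Student's test therefore uses a standard error about 10% too large, and simulated power is about 82% against 87% for Welch. With the sizes swapped, Student's standard error is √(2337 × 0.1067) = 15.8 against a correct 17.4. It then rejects more often than Welch, but only because it is too liberal.

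**The case against.** The strongest reply is that nothing in the documents shows the IR and NIR spreads to differ. Tables 2 and 3 carry one SD per endpoint, and all six sample sizes reproduce with a common SD. The expected split is near-even, and 60 was chosen to reach 17 per group, so the sizes are not simply left to chance. At 20/20 the level is 5.2% even with a twofold SD ratio. All of this stands and makes the point conditional.

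Three stronger readings are tempting, and the documents do not support them.

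- A reader might infer from the percentage SDs that the SD scales with the mean, so that the planned 20–50% differences imply SD ratios of 1.2 to 1.5 and hence an inflated false-positive rate. That mechanism gives equal SDs when the means are equal, and Student's test then holds 5%. It can support only the power result in step 5, and percentages do not by themselves establish it.
- A reader might conclude that the trial's confidence intervals will be wrong. The plan specifies none. The remark applies only if pooled-variance intervals are reported.
- A reader might lead with 28/12, where the error reaches 9.4%. That split is very unlikely under one-third shares and misses the plan's own minimum of 17. The shortfall in recruitment would then be at least as serious, and Welch's test does not cure it.

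The reading of Student's test as the pooled-variance test also rests on the ordinary meaning of its name, since the plan does not spell it out. A log transformation would be another reasonable answer if the SD really were proportional to the mean.

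**Conclusion.** The point holds in conditional form. The plan commits every NIR–IR comparison to a test that keeps its 5% level only if group sizes or SDs are about equal, and it secures neither. At splits that could plausibly arise, with assumed SD ratios up to 1.5, the true level lies between roughly 3% and 7.5%; the direction cannot be known in advance. If the SD scales with the mean and the higher-mean group is the larger, the loss is in power, about 5 points for the cytokine row at 25/15. Near 20/20, or with equal SDs, there is no practical problem. The conclusion rests on assumed SD ratios and normal data. The sample sizes in Tables 2 and 3 are not in question. Minor severity; a cheap improvement.

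**What to change.** In both paragraphs of the Statistical analysis section, replace Student's t-test with Welch's unequal-variance t-test for the NIR–IR comparisons. If confidence intervals are reported, use the matching Welch interval.

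The cost arises only if the variances are in fact equal. For a true difference of 1 SD, power falls by about 0.1–0.2 points at 17/17, 0.6–0.7 at 25/15 (0.847 to 0.841) and about 2 at 28/12 (0.805 to 0.789). The required 17 per group and the total of 60 need no change. The change should be made before group membership and endpoint data are seen together.

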### **Subjects**

A total of 60 obese, pre-diabetic women [n=30] and men [n=30] will be recruited for this study. Eligible subjects will be homogeneous in terms of the magnitude and distribution of their adiposity (BMI: 30-40 kg/m^2; waist circumference: 88-98cm for women and 100-110cm for men), age (18-45 years old), and physical activity behavior (sedentary). All subjects must be weight stable ( $\pm 3$ kg for  $\geq 6$  months) and they will be screened with a detailed health history survey. Subjects will not be taking medications known to affect lipid or glucose metabolism. Anyone with evidence and/or history of cardiovascular or metabolic diseases will be excluded. All women will be pre-menopausal and will have regularly occurring menses. To avoid potential confounding hormonal effects, all women will be studied in the early follicular phase of their menstrual cycle.

Based on past experience, we anticipate that approximately 50% of the subjects who sign an informed consent document before undergoing our more involved screening procedures will not participate in this study (largely due to being deemed ineligible after screening or because of personal reasons). Therefore, we anticipate a total of 120 subjects will sign our informed consent document.

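### The NIR vs IR t-test and the simple regressions omit sex, which the protocol names as a factor to balance without stating a method

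*Combined protocol and SAP*

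**What the plan says.** - **Group comparison.** Statistical analysis states, in each of its two paragraphs, that a Student's "t-test will be used to assess statistical significance of our major endpoints between" NIR and IR. No covariate is named.
- **Regressions.** The same section says "we will perform simple linear regression analyses to assess relationships between each of our major endpoints and insulin resistance". A multiple regression then apportions the variance of insulin resistance among the major endpoints. Sex is not listed as a predictor in either.
- **Phosphosites.** A site enters the comparison if it is "identified in more than half of the samples" and passes a fold-change filter, so some sites will have few observations per group.
- **Grouping.** Under Subject stratification, groups are formed "as defined by their glucose disposal rate (GDR) measured via hyperinsulinemic/euglycemic clamp during the experiment", with one set of cutoffs for both sexes.
- **Sex balance.** The same section says "We will make every effort to closely balance subject characteristics across the three study groups (including sex"), but gives no within-group quota, matching rule or fallback. Under Subjects, "A total of 60 obese, pre-diabetic women [n=30] and men [n=30] will be recruited for this study".
- **Other control of sex.** Under Subjects, "To avoid potential confounding hormonal effects, all women will be studied in the early follicular phase of their menstrual cycle", and the waist ranges are sex-specific. GDR is expressed per kg of fat-free mass.
- **Size.** Sample size calculations concludes that "at least 17 subjects will be required for each group in this study". For Aim 2, only IR and NIR samples are analysed.

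**The concern.** NIR vs IR is a comparison of observed groups, not randomised ones, and a subject's group is known only after the clamp. The sponsor treats sex as worth balancing, but the analysis has no provision for the case where balance is missed. If an endpoint differs by sex and the two groups hold different numbers of women, part of the NIR-IR difference is a sex difference. The error can run in either direction. Even with equal numbers, the sex difference stays in the error term of an unadjusted test. Endpoints that do not differ by sex are unbiased either way. If the choice to adjust were made after the split is seen, it would be a data-driven choice across many endpoints.

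**Working it through.** **1. The plan's own figures.** A two-sided, unadjusted two-sample t-test (noncentral t, alpha 0.05, power 0.80) gives 13, 17 and 17 per group for Table 2 and 17, 12 and 17 for Table 3. All six match. The rows that drive the sample size have a standardised effect of 20%/20% = 25%/25% = 1 SD. Power at 17 per group is 0.807.

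**2. How uneven the split could be.** Input: 30 women of 60, divided 17/17/26, with GDR unrelated to sex and no steering of recruitment. The exact multivariate hypergeometric distribution gives these probabilities that NIR and IR differ in number of women:
- by 3 or more: 0.40
- by 5 or more: 0.125
- by 7 or more: 0.026

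**3. Bias.** Bias = (difference in women / 17) x sex effect. The documents give no sex effects, so 0.5-1.0 within-sex SD is assumed.
- 10 vs 7 women: 3/17 x 0.5 = 0.09 SD; 3/17 x 1.0 = 0.18 SD
- 11 vs 6 women: 5/17 x 0.5 = 0.15 SD; 5/17 x 1.0 = 0.29 SD

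The planned effect is 1 SD.

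**4. Type I error at a fixed split** (simulation, 17 per group, sex effect 0.5 to 1.0 SD):

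| Women, NIR vs IR | t-test | group + sex |
|---|---|---|
| 8 vs 8 | 4.4% to 2.8% | about 5% |
| 10 vs 7 | about 5% | about 5% |
| 11 vs 6 | 6% to 9% | about 5% |
| 12 vs 5 | 8% to 16% | about 5% |

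Averaged over chance splits, the t-test is at about 5%.

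**5. If GDR also differs by sex.** This is an assumption; 60 subjects are cut 20/20/20 by GDR. A shift of 0.25 SD gives an average t-test error of 5.4-6.7%, and 0.5 SD gives 7-12%. The 60-subject simple regressions give 5.8-7.0% and 7-13%. Regressions restricted to IR and NIR subjects, as in Aim 2, behave similarly. With sex in the model, all are about 5%.

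**6. Power for a 1 SD effect.** The result depends on whether the Table 2 SD is within-sex or mixed-sex, which the protocol does not say. For the mixed-sex reading, within-sex SD = 1/sqrt(1 + d²/4), where d is the sex effect in within-sex SD.

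| Case | Table 2 SD read as | t-test | group + sex |
|---|---|---|---|
| 8 vs 8, d = 0.8 | within-sex | 0.76 | 0.81 |
| 8 vs 8, d = 0.8 | mixed-sex | 0.82 | 0.86 |
| Averaged over chance splits, d = 0.5 to 1.0 | within-sex | 0.78 to 0.71 | about 0.79 |
| Averaged over chance splits, d = 0.5 to 1.0 | mixed-sex | about 0.81 | 0.82 to 0.87 |

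**7. Cost when sex has no effect.** With equal groups and half of the subjects women, the noncentrality is sqrt(17/2) x sqrt(1 - D²), where D is the difference in the proportion of women, on 34 - 3 = 31 df. At 12 vs 5, D = 7/17 = 0.412 and the noncentrality is 2.915 x 0.911 = 2.66. Power falls from 0.807 to 0.806 (8 vs 8), 0.794 (10 vs 7), 0.770 (11 vs 6) and 0.730 (12 vs 5). The largest loss shown is 0.807 - 0.730 = 0.08.

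For a phosphosite found in 18 of 34 samples (assumed 9 per group), an effect with power 0.80 unadjusted has 0.79 adjusted at 5 vs 4 women, 0.75 at 6 vs 3, 0.64 at 7 vs 2 and 0.42 at 8 vs 1.

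**The case against.** The case for leaving the plan alone has real weight. A t-test is a defensible primary analysis in a small mechanistic study, and under chance imbalance alone it keeps its level. The 8-16% error belongs to a 12 vs 5 split, and a difference that large has probability 0.026. At the more likely 10 vs 7 the error is 5%, and near balance the test is conservative. If the Table 2 SD is a mixed-sex SD, average power already meets 0.80, so adjustment is an efficiency gain and does not repair a shortfall. The design also limits the role of sex through the cohort quota, sex-specific waist ranges, a single cycle phase, GDR per kg of fat-free mass and the undertaking to balance. Recruitment could be steered by sex.

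All of this stands, and it rules out two stronger readings that a reader might infer. One is that the plan simply leaves sex to chance. It does not: it states an intention to balance, and what is missing is the method. The other is that the t-test is invalid here. That would need both a sex effect on the endpoint and a GDR difference by sex, and the documents give neither.

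What remains is that none of these measures fixes the split between NIR and IR. The trial will be read from one realised split, and an error rate that is correct on average does not remove bias from that split. The multiple regression does not fill the gap, because its stated predictors are the endpoints.

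**Conclusion.** The concern holds as a recommended, inexpensive improvement. That sex is absent from the t-test and the simple regressions, and that no balancing method is stated, is plain from the text. The consequences are conditional. The bias of 0.15-0.29 SD at 11 vs 6 women, and the gain in average power from about 0.01 to 0.08, rest on an assumed sex effect of 0.5-1.0 within-sex SD. Systematic inflation of type I error rests on a further assumption about GDR and sex.

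A reader might also infer that the sample size is wrong. It is not: Tables 2 and 3 reproduce exactly, and near balance the target of 60 need not change.

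**What to change.** Amend both paragraphs of Statistical analysis:

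- **Targeted endpoints.** Make the primary NIR vs IR comparison a linear model with group and sex. Report the group coefficient with its 95% CI, and the numbers of women and men in each group.
- **Simple regressions.** Add sex as a covariate: whole cohort for Aim 1, IR and NIR subjects for Aim 2.
- **Phosphosites.** Use the same model only where both groups contain at least a prespecified minimum of each sex; otherwise keep the planned t-test. In the example of 9 per group, a minimum of three of each sex would hold the power loss to about 0.05 (0.80 to 0.75, at 6 vs 3).
- **Unchanged.** The multiple regression, which asks about relative contribution, and the phosphosite filters.

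Possible wording: *Targeted endpoints will be compared between NIR and IR with a linear model containing group and sex. Simple regressions on insulin resistance will include sex as a covariate. Phosphosites will be analysed with the same model where each group includes at least [prespecified number] women and men, and otherwise by t-test.*

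The cost is a few sentences and one degree of freedom, since the 30/30 quota already requires sex to be recorded. Where sex has no effect, the power loss is under 0.01 at balance and up to 0.08 at 12 vs 5 women. The model also assumes the same NIR-IR difference in women and men, which should be stated in the plan.

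### No adjustment across sites is stated for the untargeted phosphosite comparisons; the 1.5-fold rule lowers the share of false sites but sets no bound on it

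*Combined protocol and SAP*

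**What the plan says.** The Statistical analysis section opens its paragraph on untargeted work with "For our untargeted analyses, the false discovery rate (FDR) for both proteins and peptides will be set to 0.01". The next sentence sets the localization probability above which a phosphosite counts as identified.

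Two entry conditions follow: "To be used in comparisons between groups, phosphorylation sites need to satisfy the following criteria", namely "identified in more than half of the samples" and "with a fold change (or difference) greater than 1.5 between comparisons".

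The test is then named. "For comparisons between groups for both our untargeted and target endpoints", it is Student's t-test between NIR and IR at P<=0.05. No adjustment across sites appears there or elsewhere in the document.

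The paragraph headed "Unbiased proteomic analysis of the phosphoproteome in skeletal muscle" describes the laboratory work and refers onward for the rest: "Mass spectrometry, data analysis and bioinformatics will all also be performed as detailed previously by" the collaborating laboratory, with two cited papers. It also states the follow-up: "We will aliquot muscle protein lysates and use some aliquots to perform western blot analysis on the proteins with significant differences" between the two groups.

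The Background speaks of hundreds of tyrosine phosphorylation sites. Sample size calculations gives the proteomic work no sizing of its own; it reuses the subjects needed for the targeted endpoints, at least 17 per group.

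**The concern.** One per-test threshold of 0.05 serves both a handful of targeted endpoints and hundreds of sites. Nothing stated limits how many of the declared sites are chance findings. A reader who sees 0.01 called a false discovery rate may believe that the group comparisons are covered.

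Hypothesis 2B, which looks for novel differences between the groups, rests on this list, and the list decides which proteins go to western blot. The blots use aliquots of the same subjects' lysates. They can expose an assay artefact but cannot remove a chance difference between these two sets of subjects.

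A second matter bears on any repair. Fold change is computed from the same group difference that the t-test examines, so the P values of sites that survive the filter are no longer 5% tests.

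**Working it through.** **The plan's own figure.** Table 3 (difference 20%, SD 20%, power 0.8, alpha 0.05) gives 17 per group. The two-sided noncentral t calculation also gives 17 (power 0.807). The sample size reproduces and is not in question.

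**Inputs from the documents.** n = 17 per group (Table 3); P<=0.05, taken as two-sided; fold change above 1.5, so |d| > log2(1.5) = 0.585.

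**Assumptions.** Independent sites; normal log2 intensities; equal SD s at every site; truly changed sites differ 2-fold (1 log2 unit); a fraction f of sites is truly changed. The plan gives neither s nor f.

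**Step 1: chance that a site is declared.** The observed difference d has standard error s x sqrt(2/17) = 0.343s. A site is declared if |d| > 0.585 and |t| exceeds the 5% critical value on 32 df. The joint probability is the normal tail integrated over the chi-square distribution of the pooled variance.

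**Step 2: false share.** (1-f) x null / [(1-f) x null + f x power]. At s = 0.8 and f = 0.05: 0.95 x 0.02955 = 0.0281; 0.05 x 0.926 = 0.0463; 0.0281/0.0744 = 38%.

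| log2 SD | null probability | power, 2-fold | false share, f = 5% | range, f = 20% to 2% |
|---|---|---|---|---|
| 0.5 | 0.00065 | 0.992 | 1% | 0.3-3% |
| 0.55 | 0.00193 | 0.986 | 4% | 0.8-9% |
| 0.6 | 0.00448 | 0.978 | 8% | 2-18% |
| 0.8 | 0.02955 | 0.926 | 38% | 11-61% |
| 1.0 | 0.04743 | 0.805 | 53% | 19-74% |

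**Step 3: where the documents' SDs fall.** The targeted-endpoint SDs in Tables 2 and 3 run from 20% to 40%. With sqrt(ln(1+CV^2))/ln 2 these become log2 SD 0.29 to 0.56. At 0.556 the false share is 0.9-9.7% as f falls from 20% to 2%; at 0.29 it is essentially zero. So the documents' own SDs give 0-10% at 17 per group.

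**Step 4: incomplete detection.** The detection rule does not say whether samples are pooled or counted per group. At SD 0.55, a site with 13 values per group has a false share of 3-25%. With 9 per group, a boundary case and not typical, it is 8-52%.

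**Step 5: P values after the filter.** Among null sites that pass the 1.5-fold rule, P<=0.05 occurs in 100% (SD 0.6), 90% (0.8: 0.02955/0.0330) and 54% (1.0).

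**Step 6: where an adjustment must sit.** This was simulated with 600 sites, 30 truly 2-fold, 17 per group. Benjamini-Hochberg (BH) at 5% applied only to survivors of the filter leaves about 37% false at SD 0.8 and again at SD 1.0. Applied to all sites, it gives about 5% or less at every SD run.

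**The case against.** **The filter protects.** This is partly right. With 5% of sites changed, P<=0.05 alone would give a false share of 49%, 50% and 54% at SD 0.5, 0.8 and 1.0; adding the 1.5-fold rule gives 1%, 38% and 53%. A reader might infer that making fold change an entry condition is what leaves the false share uncontrolled. The text does not support that. A declared site must meet both conditions, the list is the same in either order, and the second condition can only shorten it. The gap is the absent adjustment. The order matters only for how survivors' P values are read and for where an adjustment is placed.

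**The high figures are assumed.** This stands. The documents give no per-site SD and no fraction changed. At 17 per group, passing one half needs roughly SD 0.8 with 2% of sites changed, or SD 1.0 with 5%.

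**The cited papers may adjust.** They may. Only the statement that the plan itself gives no adjustment can be supported.

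**This is discovery work.** That argues for a looser level or for an exploratory label. It does not argue for leaving the level unstated, since the plan selects proteins for follow-up by significance.

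**Conclusion.** The concern holds as a gap in the stated analysis: site-level comparisons at P<=0.05, no adjustment across sites, and a 0.01 rate that belongs to identification. The 1.5-fold rule reduces false sites without bounding their share.

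The size is conditional on the assumptions listed in the working. The share is small if per-site SD resembles the targeted endpoints and detection is near complete. It can exceed half if SD is higher and few sites truly change. A reader might infer that most declared sites will be false; the documents do not show this, because SDs above about 0.56 are assumptions. Equally, nothing in the plan rules it out.

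This should be fixed before the data are analysed. It concerns the list of untargeted sites only.

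**What to change.** In the Statistical analysis section:

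1. Test every site that passes the detection rule, on log2 intensity, with no fold-change condition on entry.
2. Declare significance by BH at a level fixed in advance (5%, or 10% for discovery) across all such sites, separately within each tissue and condition analysed. Hypothesis 2B names muscle and adipose tissue, and biopsies are taken before and during insulin infusion.
3. Apply fold change above 1.5 afterwards, as a reporting criterion. State that formal control belongs to the full BH list.
4. Label 0.01 as the identification rate.
5. List sites with P<=0.05 that miss BH as exploratory.

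**Cost.** The wording and code are minor; the loss of declared sites can be real. In the simulation of 600 sites with 30 truly changed:

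| log2 SD | true sites found: plan / BH 5% | false share: plan / BH 5% |
|---|---|---|
| 0.5 | 29.8 / 29.7 | 1% / 5% |
| 0.8 | 27.7 / 17.2 | 37% / 5% |
| 1.0 | 24.2 / 6.6 | 52% / 5% |

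BH at 10% finds 20.9 (SD 0.8) and 10.3 (SD 1.0), with 9-10% false. At low SD the full BH list can hold more false sites than the plan's rule: BH gives a stated bound, not always a cleaner list.

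Fold change after BH is itself a selection. In an unfavourable mix (SD 0.25 or 1.0, 120 of 600 sites truly 1.35-fold) the full BH list had 4% false and the fold-change subset 18%. This is why the full list should be reported.
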